## 6.3. Analysis Populations

### 6.3.1. Safety Population

The safety population includes all subjects who received study vaccination.

### 6.3.2. Modified Intent-to-Treat (mITT) Population

The modified intent-to-treat (mITT) population includes all subjects who received study vaccination and contributed both pre- and at least one post-vaccination venous blood samples for immunogenicity testing (HAI and Neut antibody assays) for which valid results were reported. For analyses using the mITT population, any subject receiving a product that is different than the one they were randomized to receive will be examined and grouped on a case by case basis.

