11.6.1 Analysis Populations

The Safety Analysis population includes all subjects who received study vaccine.

The modified intent-to-treat (mITT) population includes all subjects who received study vaccine and contributed both pre- and at least one post-study vaccination venous blood samples for HAI and Neut antibody assays for which valid results were reported. For analyses using the mITT population, subjects will be grouped based on their randomized treatment arm.

The PP population includes all subjects in the mITT subset with the following exclusions:

- Data from all available visits for subjects found to be ineligible at baseline.
- Data from all visits subsequent to major protocol deviations, such as:
 - Receipt of non-study licensed, live vaccine within 30 days before or after study vaccination,
 - Receipt of non-study licensed, inactivated vaccine within 14 days before or after study vaccination,
 - Receipt of immunosuppressive therapy (e.g., corticosteroids) within 30 days before or after study vaccination.
- Data from any visit that occurs substantially out of window.

For analyses using the PP population, subjects will be grouped based on study vaccination received.

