### 6.3.3. Per Protocol Population

The per-protocol (PP) population includes all subjects in the mITT population with the following exclusions:

- Data from all available visits for subjects found to be ineligible at baseline;
- Data from all visits subsequent to major protocol deviations such as:
  - Receipt of non-study licensed, live vaccine within 30 days before or after study vaccination,
  - Receipt of non-study licensed, inactivated vaccine within 14 days before or after study vaccination,
  - Receipt of immunosuppressive therapy (e.g., corticosteroids) within 30 days before or after study vaccination.
- Data from any visit that occurs more than one day out of window:
  - Visit 4 data collected before 5 days or after 10 days post vaccination;
  - Visit 6 data collected before 20 days or after 29 days post vaccination;
  - Visit 10 data collected before 166 days or after 195 days post vaccination.

Analyses will be conducted using the PP population only if 10% or more of subjects are excluded from a primary or secondary analysis timepoint. For analyses using the PP population, subjects will be grouped based on study vaccination received.

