### 7.2. Protocol Deviations

A summary of subject specific protocol deviations will be presented by the deviation category and deviation type, study group, and stratum for all enrolled subjects in [Table 8](#). Major deviations that will be reviewed for possible exclusion of immunogenicity results from the PP population include deviations related to eligibility/enrollment, follow-up visit schedule, and receipt of exclusionary vaccines or medications. All subject-specific protocol deviations and non-subject-specific protocol deviations will be included in [Listing 3](#) and [Listing 4](#).

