## **11. TECHNICAL DETAILS**

SAS version 9.4 or above will be used to generate all tables, figures and listings.

**12. SUMMARY OF CHANGES IN THE CONDUCT OF THE STUDY OR  
PLANNED ANALYSES**

This SAP does not include any changes from the analyses described in the protocol.

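### SAP 6.3.2 lets subjects given the wrong product be grouped case by case in the mITT analysis, against the protocol's as-randomized rule and without declaring the change

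*SAP*

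**What the plan says.** Protocol 11.6.1 fixes the grouping rule: "For analyses using the mITT population, subjects will be grouped based on their randomized treatment arm". It states no exception.

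SAP 6.3.2 keeps the protocol's definition of who belongs to the mITT set but changes how some members are grouped. A subject whose product is "different than the one they were randomized to receive will be examined and grouped on a case by case basis". Nothing more is said about criteria, timing, blinding or who decides.

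SAP section 12 then states: "This SAP does not include any changes from the analyses described in the protocol".

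The two documents agree on the PP set. The SAP says "For analyses using the PP population, subjects will be grouped based on study vaccination received", and protocol 11.6.1 has the same rule.

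**The concern.** The mITT set is where an immunogenicity comparison is normally protected by randomization, and that protection depends on leaving subjects where randomization put them. A rule to be settled subject by subject takes the grouping decision out of the finalized text. Protocol 11.6 requires the SAP to be final before unblinding so that such decisions are closed by then; this one stays open.

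The open rule also sits in a set that matters. SAP section 8 runs the primary immunogenicity endpoints on mITT. SAP 6.3.3 runs PP analyses only if at least 10% of subjects are excluded at a primary or secondary timepoint, whereas protocol 11.4.2 expects about 3% to be excluded from the PP analysis of the primary immunogenicity outcome. If 6.3.3 governs, mITT may be the only set analysed. SAP section 8 also says that all immune responses are analysed on PP; that is a separate inconsistency, and mITT remains a primary-endpoint set either way.

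Section 12 adds to the problem. SAP section 1 promises that the clinical study report will explain departures from the SAP. A regrouping made under 6.3.2 follows the SAP, so nothing would prompt the report to tell readers that the protocol's rule was not applied.

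**Working it through.** **Text comparison**

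| Point | Protocol 11.6.1 | SAP |
|---|---|---|
| mITT grouping | Randomized arm, no exception | 6.3.2: case by case if another product was received |
| PP grouping | Vaccination received | 6.3.3: vaccination received |
| Declared change | – | Section 12: none |

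The first row is a direct conflict, and section 12 is incorrect on it.

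**What could be known when the decision is made.** SAP 6.2.1 generates the topline tables after titers through Day 180 are received. Listing 1 sets randomized group beside product received. The documents do not say that the grouping decision must come before either is available. It may come earlier, but nothing requires it.

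**Size.** The plan gives no figure for this point, so there is none to reproduce. For illustration, take the 50% rows of SAP Table 7: 0.50 versus 0.83 at 30 per arm (15 and 25 responders) and 0.50 versus 0.77 at 50 per arm (25 and, rounded, 38 responders). Suppose one subject randomized to unadjuvanted vaccine received AS03 and is moved to the paired adjuvanted arm of the same stratum. Both numerators and both denominators change.

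With n per arm, x0 unadjuvanted and x1 adjuvanted responders:

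- As randomized: x1/n − x0/n
- One responder moved: (x1 + 1)/(n + 1) − (x0 − 1)/(n − 1)
- One non-responder moved: x1/(n + 1) − x0/(n − 1)

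| n | As randomized | Responder moved | Non-responder moved |
|---|---|---|---|
| 30 | 25/30 − 15/30 = 33.3 points | 26/31 − 14/29 = 35.6 (+2.3) | 25/31 − 15/29 = 28.9 (−4.4) |
| 50 | 38/50 − 25/50 = 26.0 points | 39/51 − 24/49 = 27.5 (+1.5) | 38/51 − 25/49 = 23.5 (−2.5) |

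With two responders moved, the shifts are +4.6 points (27/32 − 13/28 = 37.9) and +3.0 points (40/52 − 23/48 = 29.0).

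In these examples the direction depends on whether the subject responded, which is why the decision should not be open once titers are in hand.

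**The case against.** The strongest reply is that little hangs on the sentence. The mITT set feeds descriptive displays (Tables 22 and 24; Figures 2, 4, 10, 12 and 18). SAP 8.1 plans no formal hypothesis testing, and the regression models in SAP 8.3.2 are specified for PP, where the protocol itself groups by vaccination received. Each subject gets one dose in clinic, so swaps should be rare, and Listing 1 would make them visible. Assay staff are blinded to adjuvant status, subject and visit (SAP 4.4.6). All of this stands and limits the size. It does not remove the conflict, and laboratory blinding does not bind whoever decides the grouping.

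Four stronger readings are tempting, but the documents do not support them.

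- **That the SAP does regroup these subjects, or that the randomized comparison is broken.** The sentence permits regrouping; a subject may equally be left in the randomized arm. With descriptive mITT summaries and few expected swaps, the comparison is exposed to discretion, not shown to be invalid.
- **That the PP set fails to catch dosing errors.** SAP 7.2 says that the deviations reviewed "include deviations related to eligibility/enrollment, follow-up visit schedule, and receipt of exclusionary vaccines or medications", and SAP Table 8 has a treatment administration category not named there. But that list is introduced as inclusive, and the exclusion lists are open as well: "Data from all visits subsequent to major protocol deviations such as" in the SAP and "Data from all visits subsequent to major protocol deviations, such as" in the protocol, with the same three examples. A serious administration error can be treated as a major deviation under that wording, and a swap between the two products is handled by as-received grouping. Protocol 6.1.3 also bars use of product after a temperature excursion unless it is cleared. What remains is incomplete drafting: the Listing 5 note wants exclusion reasons to match the SAP text, and neither 6.3.3 nor Table 15 names this one.
- **That one subject is worth 3.3 points in an arm of 30 or 2 points in an arm of 50.** That divides by a fixed denominator. Removing one responder from 15/30 gives 14/29 = 48.3%, a change of 1.7 points; from 25/50 it gives 24/49 = 49.0%, a change of 1.0 point.
- **That 1–2% of subjects, 4 to 8 of 420, would be affected.** The documents give no such rate, and the figure would mix product swaps, the only errors SAP 6.3.2 concerns, with all preparation errors.

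**Conclusion.** The concern holds for the mITT sentence. SAP 6.3.2 contradicts protocol 11.6.1, leaves the grouping open after product and titers can be known, and is covered by an incorrect statement of no change in SAP section 12. This rests on the text alone.

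The size rests on assumptions: one swapped subject, a control response of 50%, and adjuvanted response near 83% (30 per arm) or 77% (50 per arm). Under these, one responder moves the between-arm difference by about 1.5 to 2.3 points, and one non-responder by 2.5 to 4.4 points the other way. With no swaps the effect is nil. The point is worth correcting because it concerns a primary-endpoint population and costs almost nothing, not because a large bias is expected. There is no corresponding protocol–SAP conflict for the PP set.

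**What to change.** In SAP 6.3.2, replace the case-by-case sentence with the protocol's rule that mITT subjects are analysed in the arm to which they were randomized. Section 12 is then correct on this point. If the sponsor prefers another rule, write it out in 6.3.2 with criteria, finalize it before unblinding, and declare and justify it in section 12.

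Leave PP grouping by vaccination received as it is. Do not add receipt of the wrong product as a PP exclusion: both documents keep such subjects in PP and group them by what they received, so the exclusion would create a new departure from the protocol.

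As a minor option, SAP 7.2 could name the Table 8 treatment administration deviations among those reviewed, before unblinding, for possible PP exclusion. If this is done, Table 15 needs a matching reason at each timepoint so that it agrees with Listing 5.

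The main change is one sentence and needs no new data. The option adds a phrase and a few table rows, and the PP set might lose a few subjects.

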### 6.3.3. Per Protocol Population

The per-protocol (PP) population includes all subjects in the mITT population with the following exclusions:

- Data from all available visits for subjects found to be ineligible at baseline;
- Data from all visits subsequent to major protocol deviations such as:
  - Receipt of non-study licensed, live vaccine within 30 days before or after study vaccination,
  - Receipt of non-study licensed, inactivated vaccine within 14 days before or after study vaccination,
  - Receipt of immunosuppressive therapy (e.g., corticosteroids) within 30 days before or after study vaccination.
- Data from any visit that occurs more than one day out of window:
  - Visit 4 data collected before 5 days or after 10 days post vaccination;
  - Visit 6 data collected before 20 days or after 29 days post vaccination;
  - Visit 10 data collected before 166 days or after 195 days post vaccination.

Analyses will be conducted using the PP population only if 10% or more of subjects are excluded from a primary or secondary analysis timepoint. For analyses using the PP population, subjects will be grouped based on study vaccination received.

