- Vital signs, including oral temperature, pulse and BP, may be obtained if indicated. Subjects must not eat or drink anything hot or cold, or smoke within 10 minutes prior to taking oral temperature.

- A targeted physical examination, including an assessment for signs suggestive of PIMMCs, may be performed, if indicated based on review of interim medical history, by a study clinician licensed to make medical diagnoses and listed on the Form FDA 1572 as the site PI or sub-investigator.
- The study vaccination site will be examined.
- At sites processing blood for PBMCs isolation, approximately 24 mL of venous blood will be collected for future research.

Note: This visit may be performed as a phone call assessment for sites not processing blood for PBMCs isolation. Study personnel will contact these subjects by phone to review their Memory Aid information and solicit any AE/SAEs and concomitant medications (including solicitation for receipt of any non-study influenza vaccines). Based on the information collected, subjects may be asked to return to the clinic for evaluation.

8.2.3 Visit 04, Day 8, Clinic Visit (Window: Day 8-1/+2 days post study vaccination)

- Interim medical history, including an assessment for new medical conditions, stability of chronic diseases and symptoms suggestive of PIMMCs, will be obtained by interview of subjects and any changes since the previous clinic visit or phone call will be noted.
- All concomitant medications (including solicitation for receipt of any non-study influenza vaccines) will be recorded on the appropriate DCF.
- All AE/SAEs will be recorded on the appropriate DCF.
- Memory Aid information will be reviewed with subjects.
- Vital signs, including oral temperature, pulse and BP, may be obtained if indicated. Subjects must not eat or drink anything hot or cold, or smoke within 10 minutes prior to taking oral temperature.
- A targeted physical examination, including an assessment for signs suggestive of PIMMCs, may be performed, if indicated based on review of interim medical history, by a study clinician licensed to make medical diagnoses and listed on the Form FDA 1572 as the site PI or sub-investigator.
- The study vaccination site will be examined.

- Approximately 10 mL of venous blood will be collected for clinical safety labs (WBC, Hgb, PLT, ALT, T. Bili, Cr) to be performed by the central (clinical) laboratory.

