8.2.5 Visit 06, Day 22, Clinic Visit
(Window: Day 22+7 days post study vaccination)

- Interim medical history, including an assessment for new medical conditions, stability of chronic diseases and symptoms suggestive of PIMMCs, will be obtained by interview of subjects and any changes since the previous clinic visit or phone call will be noted.
- Concomitant medications (including solicitation for receipt of any non-study influenza vaccines) will be recorded on the appropriate DCF.
- All AE/SAEs will be recorded on the appropriate DCF.
- A targeted physical examination, including an assessment for signs suggestive of PIMMCs, may be performed, if indicated based on review of interim medical history, by a study clinician licensed to make medical diagnoses and listed on the Form FDA 1572 as the site PI or sub-investigator.
- Approximately 15 mL of venous blood will be collected for serological assays. Approximately 5 mL of this venous blood sample will be designated for future research.
- At sites processing blood for PBMCs isolation, approximately 24 mL of venous blood will be collected for future research.

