8.2.7 Visit 08, Day 91, Clinic Visit
(Window: Day 91±14 days post study vaccination)

- Interim medical history, including an assessment for new medical conditions, stability of chronic diseases and symptoms suggestive of PIMMCs, will be obtained by interview of subjects and any changes since the previous clinic visit or phone call will be noted.
- Receipt of any non-study influenza vaccines will be recorded on the appropriate DCF.

- AEs limited to SAEs and MAAEs, including NOCMCs and PIMMCs, that have occurred since the previous clinic visit or phone call will be solicited.
- A targeted physical examination, including an assessment for signs suggestive of PIMMCs, may be performed, if indicated based on review of interim medical history, by a study clinician licensed to make medical diagnoses and listed on the Form FDA 1572 as the site PI or sub-investigator.
- At sites processing blood for PBMCs isolation, approximately 56 mL of venous blood will be collected for future research.

Note: This visit may be performed as a phone call assessment for sites not processing blood for PBMCs isolation. Study personnel will contact these subjects by phone to solicit receipt of any non-study influenza vaccines and AEs limited to SAEs and MAAEs, including NOCMCs and PIMMCs, that have occurred since the previous clinic visit or phone call. Based on the information collected, subjects may be asked to return to the clinic for evaluation.

8.2.8 Visit 09, Day 121, Safety Follow-up, Phone Call (Window: Day 121±14 days post study vaccination)

Subjects will be contacted by phone to query for safety events and receipt of any non-study influenza vaccines. AEs limited to SAEs and MAAEs, including NOCMCs and PIMMCs, that have occurred since the previous clinic visit or phone call will be solicited. Based on the information collected, subjects may be asked to return to the clinic for evaluation.

8.2.9 Visit 10, Day 181, Clinic Visit (Window: Day 181±14 days post study vaccination)

- Interim medical history, including an assessment for new medical conditions, stability of chronic diseases and symptoms suggestive of PIMMCs, will be obtained by interview of subjects and any changes since the previous clinic visit or phone call will be noted.
- Receipt of any non-study influenza vaccines will be recorded on the appropriate DCF.
- AEs limited to SAEs and MAAEs, including NOCMCs and PIMMCs, that have occurred since the previous clinic visit or phone call will be solicited.

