### 4.4.5. Selection and Timing of Dose for Each Subject

Each subject is to be randomly assigned to a study group which will define the receipt of adjuvant for the study vaccination administered on Day 1. Study groups are defined by a combination of prior receipt of 2013 A/H7N9 IIV and study product randomization as shown in [Table 1](#).

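### The SAP's per-protocol lower limit for Visit 10 (166 days) omits the one-day tolerance that the SAP's own rule grants; it should be 165 days

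*SAP*

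**What the plan says.** SAP Section 6.3.3 sets the visit-timing exclusion for the PP population as a general rule: "Data from any visit that occurs more than one day out of window". Three bullets beneath it turn the rule into limits in days after vaccination:

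- for Visit 4, results from 5 to 10 days are kept;
- for Visit 6, results from 20 to 29 days are kept;
- for the six-month visit, the exclusion reads "Visit 10 data collected before 166 days or after 195 days post vaccination".

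The visit windows come from the protocol:

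- Visit 4, Section 8.2.3: "Window: Day 8-1/+2 days post study vaccination"
- Visit 6, Section 8.2.5: "Window: Day 22+7 days post study vaccination"
- Visit 10, Section 8.2.9: "Window: Day 181±14 days post study vaccination"

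The schedule in SAP Table 2 repeats the same windows. SAP Section 4.4.5 fixes the day numbering, with the "study vaccination administered on Day 1".

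**The concern.** The three bullets are presented as the application of one rule, so each should equal the protocol window widened by one day at both ends. The Visit 10 bullet does not: its lower limit is the bare edge of the window. A sample taken 165 days after vaccination is exactly one day early. The rule keeps it and the listed limit drops it, so a programmer has two conflicting instructions for the same record.

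The limit feeds several outputs:

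- the out-of-window row for PP Day 181 in SAP Table 15;
- the exclusion reasons in Listing 5, which are meant to agree with the SAP text;
- the 180-day blocks of the PP summaries in Tables 23 and 25;
- the count of excluded subjects that Section 6.3.3 compares with a 10% threshold when deciding whether PP analyses are run.

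**Working it through.** **Inputs**

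- Vaccination is Day 1 (SAP Section 4.4.5), so days after vaccination = study day − 1. The endpoint wording agrees: the Day 8, Day 22 and Day 181 visits supply the 7-, 21- and 180-day endpoints (SAP Sections 3.2.1 and 3.2.2).
- Windows: Day 8 −1/+2, Day 22 −0/+7, Day 181 −14/+14 (Protocol Sections 8.2.3, 8.2.5 and 8.2.9).
- Tolerance: one day (SAP Section 6.3.3).

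**Formulas**, in days after vaccination

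- Lower limit = study day − 1 − early allowance − 1
- Upper limit = study day − 1 + late allowance + 1

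**Results**

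| Visit | Window in days after vaccination | Lower limit by rule | Upper limit by rule | SAP limits | Agreement |
|---|---|---|---|---|---|
| 4 | 6 to 9 | 8 − 1 − 1 − 1 = 5 | 8 − 1 + 2 + 1 = 10 | 5 and 10 | both |
| 6 | 21 to 28 | 22 − 1 − 0 − 1 = 20 | 22 − 1 + 7 + 1 = 29 | 20 and 29 | both |
| 10 | 166 to 194 | 181 − 1 − 14 − 1 = 165 | 181 − 1 + 14 + 1 = 195 | 166 and 195 | upper only |

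The rule reproduces five of the six SAP limits. The exception is the Visit 10 lower limit, by one day. The length of the interval shows the same thing: a ±14 window covers 29 days, and one extra day at each end makes 31 (165 to 195 inclusive), whereas the SAP's limits cover 30 (166 to 195).

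**Other readings tried**

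The same calculation was repeated with 0, 1 and 2 days of tolerance, and with the study-day numbers taken directly as days after vaccination (no subtraction of 1).

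| Day scale | Tolerance 0 | Tolerance 1 | Tolerance 2 |
|---|---|---|---|
| Study day − 1 | 1 of 6 | 5 of 6 | 0 of 6 |
| Study day taken as days | 3 of 6 | 1 of 6 | 2 of 6 |

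No combination gives all six. The reading that produces 166 at the bottom with one day of tolerance (181 − 14 − 1 = 166 on the study-day scale) gives 181 + 14 + 1 = 196 at the top, against the SAP's 195. It also turns the Visit 4 and Visit 6 limits into 6 to 11 and 21 to 30.

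**The case against.** The arithmetic cannot be disputed, so the case on the other side is about consequence.

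- **The sample is outside the protocol window anyway.** At 165 days the visit is already a window deviation. Protocol Section 11.6.1 excludes only visits that are well out of window and sets no number, so no protocol rule is broken. This stands: the conflict is between the SAP's tolerance and the SAP's own listed limit.
- **The limit may never affect a reported result.** Section 6.3.3 runs PP analyses only if at least 10% of subjects are excluded at a primary or secondary timepoint, and the documents expect about 3% exclusion (Protocol Section 11.4.2, there for the primary immunogenicity outcome). This stands only in part, because SAP Section 8 says that all immune responses will be analysed in the PP population, without that condition.
- **The 180-day results are also shown without the exclusion.** Tables 22 and 24 have 180-day blocks for the mITT population, whose definition in Section 6.3.2 has no visit-window criterion. A 165-day sample stays in those tables. This stands for the vaccine strain.
- **No bias between arms is shown.** The limit applies equally to both arms of a blinded 1:1 randomised trial. This stands; the asymmetry is between early and late visits.
- **The cause is inferred.** The number 166 may come from mixing study days with days after vaccination. That is plausible, but it does not rescue the bullet, whose unit is stated as days post vaccination and whose upper limit would then be wrong.

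**Conclusion.** The Visit 10 lower limit contradicts the rule that it is meant to apply. The discrepancy is exactly one day (166 listed, 165 by rule), and it rests only on the day numbering, the protocol window and the one-day tolerance, all of which the documents state.

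The consequence is minor. Only samples taken at exactly 165 days are affected. That these will be a handful at most is an assumption, since the documents give no distribution of visit timing. Such samples could change membership of the Day 181 PP set, the matching entries in Table 15 and Listing 5, the 180-day PP summaries, and marginally the count toward the 10% threshold. The primary endpoints at about 21 days depend on the Visit 6 limits, which are correct. This is a correction worth making for consistency, not a threat to the trial's conclusions.

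**What to change.** In the Visit 10 bullet of SAP Section 6.3.3, replace 166 with 165, so that data collected before 165 or after 195 days are excluded. The upper limit stays as it is, and all six limits then follow the stated rule. The cost is one number in the SAP, plus a check that the program deriving the Day 181 PP flag uses the same value. If a tighter early limit at Visit 10 was intended, the SAP should state it as an exception to the one-day rule and give the reason.
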